Statistical Analysis Plan: A statistical analysis plan for each clinical domain will be made publicly available before the conclusion of enrollment. General principles of the statistical analysis are outlined here. Stage 1 will evaluate the primary outcome, percentage of patients with palliative care consults placed within 48 hours after enrollment, for an anticipated 10% of the total sample size. This initial stage is designed to determine feasibility and separation between groups. The following separations between groups, during Stage 1, would then determine trial progression to Stage 2.

- > 50% group separation: the trial would move forward to Stage 2 without modification.
- 15-50% group separation: the trial would move forward to Stage 2 with modification to the

Full Study Title: Pragmatic Trial Investigating \underline{S} urprise \underline{Q} uestion in \underline{E} nd of \underline{L} ife (SeQuEL) Care and the Effect of Prompting Palliative Care Consultation on Provider Referral Rates and Subsequent Outcomes

for Hospitalized Adults with Serious Illnesses

Primary Investigator: [name], FACP, FAAHPM

eligibility criteria, intervention, or other aspects of the study protocol.

• < 15% group separation: the trial would not move forward to Stage 2.

We are explicitly examining the separation between groups for the primary outcome at Stage 1 and have outlined the trial progression scenarios. It is anticipated that all patients will have the same data collected and will be included in the analyses for the primary, secondary, and exploratory outcomes.

Baseline demographic and clinical characteristics of the participants (i.e., age, sex, race, comorbidities, disease severity, etc.) will be compared between the control and the intervention arms using Wilcoxon rank-sum test for continuous variables and Pearson's Chi-square for categorical variables. The main analysis will be an intention-to-treat comparison of the primary outcome between patients randomized to each of the two trial groups using a Wilcoxon rank-sum test. The main analysis of the secondary outcome will be an intention-to-treat comparison of the secondary outcome of survival to 90 days between the two trial groups using a Cox Proportional-Hazards model.

13. Privacy and Confidentiality

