Given the preliminary evidence that specialist palliative care may improve the quality and quantity of time spent alive and outside of the hospital for patients with serious illness and the incomplete implementation of specialty palliative care in current clinical practice, we will evaluate the effect of prompting consideration of palliative care consultation in the electronic health record relative to actual palliative care engagement which subsequently may impact hospital-free days among hospitalized patients with ESLD.

Population and design considerations

Study Population:

Adult patients with ESLD admitted to Vanderbilt University Medical Center (VUMC) for whom the treating clinician would not be surprised if the patient died in the next 12 months.

Inclusion criteria:

- Patient is an adult (age \geq 18 years).
- Patient is admitted to the study hospital.
- Patient's treating physician, physician associate, or nurse practitioner answers "No" to a prompt in the electronic health record asking, "Would you be surprised if this patient died in the next 12 months?"
- Patient meets phenotype criteria for ESLD.

Patients will be considered to have met the "phenotype criteria" for ESLD if they meet BOTH of the following criteria:

1. Electronic health record contains one or more of the following ICD-10 codes for a diagnosis of a cause of end-stage liver disease within the last 5 years:

- PI: [name]
 - ICD10 B18.0-Chronic viral hepatitis B with delta-agent
 - ICD10 B18.1-Chronic viral hepatitis B without delta-agent
 - ICD10 B18.2-Chronic viral hepatitis C
 - ICD10 B18.8-Other chronic viral hepatitis
 - ICD10 B18.9-Chronic viral hepatitis, unspecified
 - ICD10 B19.10-Unspecified viral hepatitis B without hepatic coma
 - ICD10 B19.11-Unspecified viral hepatitis B with hepatic coma
 - ICD10 B19.20-Unspecified viral hepatitis C without hepatic coma
 - ICD10 B19.21-Unspecified viral hepatitis C with hepatic coma
 - ICD10 K70.0-Alcoholic fatty liver
 - ICD10 K70.2-Alcoholic fibrosis and sclerosis of liver
 - ICD10 K70.30-Alcoholic cirrhosis of liver without ascites
 - ICD10 K70.31-Alcoholic cirrhosis of liver with ascites
 - ICD10 K71.7-Toxic liver disease with fibrosis and cirrhosis of liver
 - ICD10 K73(group)-Chronic hepatitis, not elsewhere classified
 - ICD10 K74.0-Hepatic fibrosis
 - ICD10 K74.1-Hepatic sclerosis
 - ICD10 K74.2-Hepatic fibrosis with hepatic sclerosis
 - ICD10 K74.3-Primary biliary cirrhosis

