- a. Palliative Care Consultation Prompt Group: A clinical decision support tool in the electronic health record will inform the treating clinician to consider a palliative care consultation. If the treating clinician feels a palliative care consultation would be indicated for the patient, the clinical decision support tool will facilitate the placement of a palliative care consultation by the treating clinician. If the treating clinician feels that a palliative care consultation would not be indicated, then the clinical decision support will record a reason why a palliative care consultation is not indicated.
- b. No Palliative Care Consultation Prompt Group: The patient's treating clinician will not receive a prompt in the electronic health record to consider a palliative care consultation.

A treating clinician can choose to place or discontinue a palliative care consultation at any time, retaining full autonomy to deliver the appropriate patient care. A patient may choose to request or decline a palliative care consultation at any time, irrespective of intervention assignment.

PI: [name]

Endpoints

Primary Endpoint

Stage 1: The primary outcome will be the percentage of patients with palliative care consults placed within 48 hours after enrollment. This initial stage is designed to determine feasibility and separation between groups. We are explicitly examining the separation between groups for the primary outcome at Stage 1 and have outlined the trial progression scenarios. It is anticipated that all patients will have the same data collected and will be included in the analyses for the primary, secondary, and exploratory outcomes.

Stage 2: The primary outcome will be hospital-free days by day 90. Hospital-free days will be defined as the number of calendar days between enrollment and day 90 in which the patient is alive and outside of an acute-care hospital. Days spent at home, at a rehabilitation facility, at a nursing facility, and at an inpatient hospice facility will count as hospital-free.

Secondary Endpoint(s)

There is one secondary outcome for this trial.

Survival to day 90. Defined as the number of calendar days in which the patient is alive between enrollment and day 90.

Exploratory Endpoint(s)

There are multiple prespecified exploratory outcomes for this trial.

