The analysis for the trial will use an intent-to-treat approach to answer the effectiveness question posed. That is, participants will be evaluated by treatment group as assigned regardless of what was delivered. All eligible participants will be included.

Statistical Approach

Our initial analysis will be descriptive in nature, summarizing information that characterizes the cohort and the outcomes. Then, we will proceed with inferential analysis to answer the main study question. Then, we will compare the secondary endpoints between study groups.

Descriptive Analysis

To characterize the study sample, baseline demographic and clinical data will be described overall and by group. Categorical variables will be described using frequencies and proportions, and continuous variables will be described using means and standard deviations, as well as medians and interquartile ranges. Missingness will be reported for each variable. Graphical summaries using extended box plots, violin plots, cumulative distribution plots, and/or histograms may be used to describe the data graphically. At a minimum, the following variables will be described at time of enrollment:

- Age (years)
- Sex (male, female, unknown)
- Race (African American, Asian/Pacific Islander, Caucasian, Multiple, Native American, Other, Unknown)
- Ethnicity (Hispanic, Non-Hispanic, Unknown)
- Comorbidities (Charlson or Elixhauser)
- MELD score

PI: [name]

We will describe all of the outcome variables overall and grouped by study arm using the same approach as for the demographic data. Summary statistics and graphical representations may be displayed, and missingness will be reported for each variable.

No statistical comparisons between groups will be done for this descriptive analysis. Please note, showing descriptive statistics stratified by treatment groups that were randomized can be easily misinterpreted, as all apparent imbalances are by definition due to chance. Descriptive statistics of all-comers need to be emphasized in randomized studies.

Main Analysis

As indicated above, the Stage 1 outcome will evaluate the proportion of patients with palliative care consults placed within 48 hours after enrollment, for an anticipated 10% of the total sample size. This initial stage is designed to determine feasibility and separation between groups. The following separations between groups, during Stage 1, would then determine trial progression to Stage 2.

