- > 50% group separation: the trial would move forward to Stage 2 without modification.
- 15-50% group separation: the trial would move forward to Stage 2 with modification to the eligibility criteria, intervention, or other aspects of the study protocol.
- < 15% group separation: the trial would not move forward to Stage 2.

We are explicitly examining the separation between groups for the primary outcome at Stage 1 and have outlined the trial progression scenarios. It is anticipated that all patients will have the same data collected and will be included in the analyses for the primary, secondary, and exploratory outcomes. The main analysis of the primary outcomes will be intention to treat comparisons between patients randomized to each of the two trial groups. For the second stage primary analysis, the likelihood ratio test from the proportional odds ordinal logistic regression model will be used to compare groups on the number of hospital-free days alive. This is a generalization of the Wilcoxon two-sample test and will be adjusted for the pre-specified baseline covariates. If a baseline covariate is missing on 5 or fewer patients, it will be imputed using the grand median (mode if categorical). If any covariates are missing on more than 5 patients, multiple imputation will be used to impute sometimes-missing covariates, and the results from the separate completed-dataset analyses will be combined using Rubin's rule.

We do not expect missingness in the outcome variables.

The main analysis of the secondary outcome (survival to day 90) will be an intention-to-treat comparison between the two trial groups using a Cox Proportional-Hazards model.

There may be missingness in secondary or implementation outcomes. The cohort for which the outcome is available will be described, along with the results of the model evaluating treatment effects in this cohort. All model results will be summarized with point estimates and 95% confidence intervals (CIs), which will be emphasized over p-values when reporting the results for secondary and implementation outcomes. No adjustments for multiplicity will be made.

Additionally, a descriptive analysis of missingness tendencies is warranted. For example, logistic regression to predict the probability of missingness of an outcome measurement with predictors that include baseline variables and other outcomes that are never missing.

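### The Cox model for 90-day survival, the only secondary outcome, names no covariates, so it gives up power that MELD, age and comorbidity could supply at no extra data cost

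*SAP*

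**What the plan says.** In the SAP, under Main Analysis, the Stage 2 proportional odds model for hospital-free days "will be adjusted for the pre-specified baseline covariates". The rules for imputing missing covariates follow in the same paragraph.

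Survival to day 90 has its own short paragraph, which specifies an "intention-to-treat comparison between the two trial groups using a Cox Proportional-Hazards model" and nothing more: no covariates and no strata. Protocol section 12 is equally brief, comparing "survival to 90 days between the two trial groups using a Cox Proportional-Hazards model".

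The SAP's endpoint section states "There is one secondary outcome for this trial", and that outcome is survival. For secondary outcomes the SAP wants point estimates with 95% confidence intervals, "which will be emphasized over p-values when reporting the results for secondary and implementation outcomes".

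The Descriptive Analysis section lists baseline variables ("At a minimum, the following variables will be described at time of enrollment"). They include age, MELD score and a comorbidity measure, with the choice between the Charlson and Elixhauser indices left open.

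**The concern.** The SAP accepts covariate adjustment for its primary outcome and gives no reason to treat survival differently. Leaving prognostic covariates out of a Cox model does not bias the test of no effect in a randomized trial. It does pull the estimated hazard ratio towards 1 relative to the effect conditional on those covariates, and power falls with it.

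Survival is where a reader will look for benefit or harm from prompting palliative care. Appendix A, section 2.0, says the pilot was underpowered for mortality, and this trial was sized on hospital-free days (Appendix A, section 12.0; SAP, Sample Size Considerations). Power for survival is whatever 776 patients happen to give.

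Reporting is affected too. The marginal and conditional hazard ratios are different quantities. A plan that puts weight on estimates and intervals should say which one it will report, and should not leave the covariates to be chosen after the data are seen.

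**Working it through.** **1. The plan's own figure.** The only sample size calculation is for hospital-free days: odds ratio 1.5, power 0.90, 388 per group. Alpha is not stated; two-sided 0.05 is assumed, which fits the 95% intervals. Whitehead's formula is

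n per group = 6(z₀.₉₇₅ + z₀.₉₀)² / [(ln OR)² (1 − Σp³)].

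With z values 1.960 and 1.282 and ln 1.5 = 0.4055, this gives 384 with no ties and 388 with Σp³ ≈ 0.012. The figure reproduces. No event count, hazard ratio or power is given for survival.

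**2. Power for survival before covariates are considered.** Schoenfeld: power = Φ(½√d × |ln HR| − 1.96). Assuming 30% average mortality, d = 776 × 0.30 ≈ 233 and ½√d = 7.63.
- HR 0.70: 7.63 × 0.3567 − 1.96 = 0.76, power 78%.
- HR 0.75: 7.63 × 0.2877 − 1.96 = 0.24, power 59%.

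**3. Unadjusted against adjusted, by simulation.** From the documents: 776 patients, 1:1 allocation, follow-up to day 90. Assumed: control 90-day mortality 25% or 35%; conditional HR 0.70, 1.43 (= 1/0.70) or 1.00; one standard normal covariate with log HR b per SD. The hazard is λ·exp(b·Z + ln HR × group), with λ set to give the stated control mortality. There were 8,000 trials per setting, each tested with a two-sided 5% Wald test. Rejection rates in percent, unadjusted / adjusted:

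| Conditional HR | Control mortality | b = 0.2 | b = 0.3 | b = 0.5 | b = 0.8 |
|---|---|---|---|---|---|
| 0.70 | 25% | 61.7 / 62.1 | 61.8 / 62.9 | 61.2 / 63.6 | 55.9 / 63.6 |
| 0.70 | 35% | 76.9 / 77.7 | 77.2 / 78.1 | 74.9 / 78.6 | 69.4 / 78.9 |
| 1.43 | 25% | 76.9 / 77.4 | 74.3 / 75.4 | 72.5 / 76.2 | 66.7 / 76.3 |
| 1.43 | 35% | 87.6 / 88.3 | 87.0 / 88.5 | 83.6 / 87.9 | 77.2 / 87.7 |
| 1.00 | 25% | 5.1 / 5.3 | 4.9 / 4.8 | 5.0 / 4.9 | 5.1 / 4.9 |
| 1.00 | 35% | 5.4 / 5.3 | 5.2 / 5.2 | 5.4 / 5.2 | 5.1 / 4.8 |

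Subtracting, the gain in points across b = 0.2, 0.3, 0.5 and 0.8 is:
- benefit: 0.4–0.8, 0.9–1.1, 2.4–3.7, 7.7–9.5;
- harm: 0.5–0.7, 1.1–1.5, 3.7–4.3, 9.6–10.5.

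The Monte Carlo standard error of each gain is 0.2 to 0.4 points.

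**4. Where the gain comes from.** It is not precision. At HR 0.70, 25% mortality and b = 0.8, the mean standard error of the log HR is 0.1557 unadjusted and 0.1561 adjusted. The estimate is what moves. Expected HR and 95% CI at 35% mortality, as mean HR × exp(±1.96 × mean SE):
- b = 0.8: 0.73 (0.56–0.94) unadjusted, 0.70 (0.54–0.90) adjusted;
- b = 0.2: 0.70 (0.54–0.91) for both.

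**5. Cross-check with three covariates.** A separate simulation (2,000 trials per setting, conditional HR 0.70, 776 patients) varied the SD of the combined covariate log-hazard. At 30% control mortality, power was 70% against 73% (SD 0.4), 62% against 70% (SD 0.8) and 53% against 71% (SD 1.1). At SD 0.8 it was 49% against 54% with 20% mortality, and 74% against 84% with 40%. With no effect (30% mortality, SD 0.8), rejection was 4.5% and 4.7%.

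**The case against.** The strongest reply is that this is a preference. A two-group Cox comparison is valid, it is prespecified in both documents, and marginal versus conditional is a legitimate choice of target. Three further points carry weight.

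- **The reading rests on silence.** The SAP introduces its primary analysis with much the same intention-to-treat, two-group wording, and that analysis is then adjusted. The phrase alone therefore does not prove that the survival model is unadjusted. This stands as a caution. Still, the adjustment sentence is tied to the proportional odds model, and if adjustment was intended for survival, the SAP still has to say so.
- **The gain may be tiny.** The pilot saw no effect on mortality, the stated primary hypothesis concerns consults and hospital-free days, and the intervention is only a prompt. Rerun at HR 0.85 (2,500 trials per setting), the gain was 0.0–0.2 points at b = 0.2, 0.0–0.6 at 0.3, 0.5–2.3 at 0.5 and 2.9–3.4 at 0.8. Adjusted power was only 19–26%. Enrollment is also limited to patients "for whom the treating clinician would not be surprised if the patient died in the next 12 months", which may narrow the prognostic spread and makes the weak end realistic. This stands: adjustment would not rescue the endpoint if the true effect is modest.
- **There is a bigger gap next door.** The covariates for the primary model are not listed anywhere either. That is true and matters more, but it is a separate point and does not answer this one.

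Since intervals are emphasized over p-values and their log-scale width is unchanged, the practical effect is a different target, not a narrower interval. That is a reason for the SAP to name its target.

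**Conclusion.** The concern holds as a low-severity matter of efficiency and specification; it is not an error of validity. Under the stated assumptions (776 patients, control mortality 25–35%, conditional HR 0.70 or 1.43), the power forgone runs from under 1 point with a weak covariate to about 10 points with a strong one. It is smaller still if the true effect is nearer 1, and nil if there is no effect. Mortality, effect size and prognostic strength are all assumed, because the documents supply none. Type I error is close to 5% either way.

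**What to change.** In the SAP, before any unblinded outcomes are seen:

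- Make the main survival analysis a Cox model with group, MELD, age and one named comorbidity index, settling the open choice at "Comorbidities (Charlson or Elixhauser").
- Apply the SAP's existing covariate imputation rules to this model.
- State that the resulting hazard ratio is conditional on those covariates, and report the unadjusted (marginal) hazard ratio and Kaplan-Meier curves beside it.
- If the team prefers the marginal hazard ratio as the main result, say so and prespecify the adjusted model as supportive.

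Two small alignments can go into the same edit: name the covariates for the primary model, and bring the Master Protocol Summary, which gives Wilcoxon and chi-square tests for secondary outcomes, into line with the Cox model.

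The cost is a few sentences. The baseline variables are already in the plan and the imputation rules are already written.
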